#### 7.2. Intracranial Progression-free survival (iPFS).

7.2.1. SYMPTOMATIC PATIENTS A+C: INTRACRANIAL PROGRESSION-FREE SURVIVAL (IPFS).

Table 156: Events type PFS

PFS	N	%	95%CI
Censored			
Event (PD/death)			
Total			

Table 157: Median/mean PFS (estimated by Kaplan-Meier)

	Median (months)	CI 95%	Mean	CI 95%
Progression-free survival				

Table 158: PFS estimated survival ratio

PFS	Events (%, total N)	Patients at risk	% estimated cumulative survival ratio	CI 95%
At 3 months				
At 6 months				
At 9 months				
At 12				
months				
At 15				
months				
At 18				
months				
At 21				
months				

Figure 21: Progression-free survival

## 7.2.2. ASYMPTOMATIC PATIENTS B: INTRACRANIAL PROGRESSION-FREE SURVIVAL (IPFS).

Table 159: Events type PFS

PFS	N	%	95%CI
Censored			
Event (PD/death)			
Total			

Table 160: Median/mean PFS (estimated by Kaplan-Meier)

	Median (months)	CI 95%	Mean	CI 95%
Progression-free survival				

Table 161: PFS estimated survival ratio

PFS	Events (%, total N)	Patients at risk	% estimated cumulative survival ratio	CI 95%
At 6 months At 12 months At 18 months At 24 months				

Figure 22: Progression-free survival

## 7.2.3. INTRACRANIAL PROGRESSION-FREE SURVIVAL (IPFS) VS SYMPTOMATIC.

Table 162: Events type PFS

Symptomatic group	
Event (PD/death)	
Censored	

1. Pearson's Chi-squared test

Table 163: Median/mean PFS (estimated by Kaplan-Meier)

	Median (months)	CI 95%	Mean	CI 95%
No				
Yes				

Table 164: PFS estimated survival ratio

PFS	Events (%, total N)	Patients at risk	% estimated cumulative survival ratio	CI 95%
No				
At 6 months				
At 12				
months				
At 18				
months				
At 24				
months				
Yes				
At 6 months				
At 12				
months				
At 18				
months				
At 24				
months				

Figure 23: Progression-free survival vs Symptomatic group

## 7.3. PRIMARY EFFICACY OBJECTIVE: RESPONSE AT 56 DAYS

Table 165: Symptomatic group (A+C): intracranial Objective Response Rate at 56 days

ORR: Intracraneal Evaluation at 56 days	N	%	95%CI
CR or PR			
SD			
NE			
Total			

Table 166: Asymptomatic group (B): intracranial Objective Response Rate at 56 days

ORR: Intracraneal Evaluation at 56 days	N	%	95%CI
CR or PR			
SD			
Total			

#### 7.3.1.INTRACRANIAL RESPONSE DURATION

Table 167: Intracranial Response Duration (months)

Duration of response	
(months)	
N	
Mean (95%CI)	
SD	
Median (95%CI)	
Range	

#### **8. A**NNEX **1**

Table 168: List of all toxicities

Patient Number Cohort AE CTCAE AE CTCAE Other AE AE Start AE Stop AE AE AE Relat  Grade Date Date ed ty
---

#### TABLE OF CONTENTS

#### 1. BASELINE CHARACTERISTICS

#### **BASELINE - DEMOGRAPHIC DATA**

Table 1: Baseline - Socio demographic data ITT

	Symptomatic (A+C)	Asymptomatic (B)	Total
Age (years)			
N			
Mean (95%CI)			
SD			
Median			
(95%CI)			
Range			
Sex			
Female			
Male			
Race			
Caucasian			
Latin			

Table 2: Baseline - Physical characteristics ITT

	Symptomatic (A+C)	Asymptomatic (B)	Total
Phototype (n(%))			
Type I			
Type II			
Type III			
Type IV			
UK			
Weight (kg)			
N			
Mean (95%CI)			
SD			
Median (95%CI)			
Range			
Height (cm)			
N			
Mean (95%CI)			
SD			
Median (95%CI)			
Range	·		

	Symptomatic (A+C)	Asymptomatic (B)	Total
Systolic Blood Pressure (mmHg)	(-1-5)		
N			
Mean (95%CI)			
SD			
Median (95%CI)			
Range			
Diastolic Blood Pressure (mmHg)			
N			
Mean (95%CI)			
SD			
Median (95%CI)			
Range			
Temperature (°C)			
N			
Mean (95%CI)			
SD			
Median (95%CI)			
Range			
Respiratory rate (BPM)			
N			
Mean (95%CI)			
SD			
Median (95%CI)			
Range			
Pulse Rate (BPM)			
N			
Mean (95%CI)			
SD			
Median (95%CI)			
Range			
ECOG (n(%))			
0			
1			
2			
Barthel index (categorical), (n(%)),			
previous to November 2020			
•			
Barthel index (Arbitrary units, scale			
0-100)			
N			
Mean (95%CI)			
SD			
Median (95%CI)			
Range			
Barthel index modified, from			
November 2020			
Barthel index modified (Arbitrary			
units, scale 0-20), from November			
2020			
N			

Symptomatic (A+C)	Asymptomatic (B)	Total

#### 1.1. BASELINE CURRENT MELANOMA

Table 3: Metastases ITT

	Symptomatic (A+C)	Asymptomatic (B)	Total
Brain Metastases			
Unique			
Multiple			
Target Brain Metastases			
1			
2			
3			
4			
5			
UK			
Extracranial Metastases			
Yes			
No			
Lung Metastases			
Yes			
No			
UK			
Lung Metastases Number			

	Cymptomatic (A+C)	Asymptomatic (D)	Total
-1	Symptomatic (A+C)	Asymptomatic (B)	iolai
1 2			
3			
4			
>5			
NA/UK			
Liver Metastases			
Yes			
No UK			
Liver Metastases Number			
1			
2 3			
>5			
NA/UK			
Skin Metastases			
Yes			
No			
UK			
Skin Metastases Number			
1			
2			
3			
>5			
UK			
Bone Metastases			
Yes			
No			
UK			
Bone Metastases Number			
1			
2			
NA/UK			
Pleura Metastases			
Yes			
No			
UK			
Pleural Effusion Volume			
0			
NA/UK			
Soft Tissue Metastases			
Yes			
No			
UK			
Soft Tissue Metastases			
Number			
1			
5			
NA/UK			
Lymph Nodes Metastases			

	Symptomatic (A+C)	Asymptomatic (B)	Total
Yes			
No			
UK			
Lymph Nodes Metastases			
Number			
1			
2			
3			
>5			
UK			
NA/UK			
Peritoneum Metastases			
Yes			
No			
UK			
Peritoneum Metastases			
Number			
1			
NA/UK			
Other Metastases			
Yes			
No			
UK			
Other Metastases Number			
1			
2			
>5			
UK			
Other Metastases Specify			

#### Table 4: BRAF ITT

	Symptomatic (A+C)	Asymptomatic (B)	Total
V600E			
Missing data			_
Mutated			
Not mutated			
V600K			
Mutated			
Not mutated			
NA/UK			_
V600E/K			
Mutated			
Not mutated			
NA/UK			
V600R			
Mutated			
Not mutated			
NA/UK			
V600 other			
Mutated			

	Symptomatic (A+C)	Asymptomatic (B)	Total
Not mutated			
NA/UK			
V600 (NE)			
Mutated			
Not mutated			
NA/UK			

#### 2. PRIMARY EFFICACY OBJECTIVE

#### 2.1. RADIOTHERAPY TREATMENT

Table 5: Radiotherapy treatment. ITT

able of Radiotherapy treatment. If I			
	Symptomatic (A+C)	Asymptomatic (B)	Total
Radiotherapy treatment (Local and/or Whole Brain)			
N			
Yes			
Yes (CR)			
No			
No (CR)			
LocaL Radiation treatment			
N			
Yes			
Yes (CR)			
No			
No (CR)			
Local Radiation Treatment type			
N			
No			
Radiosurgery (RS)			
Stereotactic radiosurgery (SRS)			
Device Used			
Missing			
N			
Gamma Knife			
Accelerator Linac-Based Systems (IMRT, Rapid Arc, VMAT)			
Cyberknife			
Whole Brain Radiotherapy			
N			
Yes			
No			
No (CR)			

#### 2.2. OS ON ITT ACCORDING TO RADIOTHERAPY

Table 6: Events type OS

Radiotherapy	
Death	
Alive	

1. Pearson's Chi-squared test

Table 7: Median/mean OS (estimated by Kaplan-Meier)

	Median (months)	CI 95%	Mean	CI 95%
No				
Yes				

Table 8: OS estimated survival ratio

os	Events (%, total N)	Patients at risk	% estimated cumulative survival ratio	CI 95%
No				
At 6 months				
At 12				
months				
At 18				
months				
At 24				
months				
Yes				
At 6 months				
At 12				
months				
At 18				
months				
At 24				
months				

Figure 25: Overall survival vs Radiotherapy

#### 2.3. IPFS ON ITT ACCORDING TO RADIOTHERAPY

Table 9: Events type PFS

Radiotherapy	
PFS Event	
PD	
Censored	
Death (without previous PD)	

1. Pearson's Chi-squared test

Table 10: Median/mean PFS (estimated by Kaplan-Meier)

	Median (months)	CI 95%	Mean	CI 95%
No				
Yes				

Table 11: PFS estimated survival ratio

PFS	Events (%, total N)	Patients at risk	% estimated cumulative survival ratio	CI 95%
No				
At 6 months				
At 12 months At 18				
months At 24				
months Yes				
At 6 months				
At 12 months				
At 18 months				
At 24 months				

Figure 26: Progression free survival vs Radiotherapy

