## 5.3. Patient Inclusion and Cohort Assignment

During the screening (28 days before day 1 cycle 1) it should be assessed whether the patient is symptomatic (cohort 2) or asymptomatic (cohort 1).

Definition of Asymptomatic (cohort 1):.Patients without active symptoms secondary to brain metastases at the moment of inclusion.

After confirming that a patient fulfils all eligibility criteria of the study (inclusion/exclusion criteria), site staff will initiate the eCRF registration procedure.

Once procedure is fulfilled the site staff will receive the "Inclusion confirmation communication", and protocol-specific treatment can be initiated.

This is an open label, single arm study including two cohorts of patients, in each cohort, patients will be treated with encorafenib 450 mg once daily and binimetinib 45 mg twice daily.

After 56 days of treatment, a contrast enhanced brain MRI and CT body scan will be performed as first tumour assessment:

- Patients with PD at first evaluation in brain MRI (modified RECIST 1.1 criteria) and /or body CT scan (RECIST 1.1 criteria) will discontinue study treatment and will continue in the study for OS follow-up.
- Patients with CR in brain (modified RECIST 1.1) and no PD in the body (RECIST 1.1), will continue study treatment and will be followed every two months with contrast enhanced brain MRI and body CT scan up to 12 months. If no PD after one year, patients will be followed as per institutional criteria, and continue with the treatment.
  - o If considered by the investigator, local treatment can be done for brain CR patients, but only after confirming no safety concerns (defined as substantial deterioration of vital signs (including ECOG PS), physical examination, ECG, Lab. Values that do not recommend RT) with the three first patients treated with radiation therapy in the running phase (for more information, please see section 9.1).
- Patients with no CR and no PD in brain MRI per modified RECIST 1.1 criteria, and no PD in body per RECIST 1.1 criteria, will be treated with local RT and/or radiosurgery, and then will continue Enco and Bini. The first 3 patients will be treated in a running

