# 10. STATISTICS

# 10.1. Sample size calculation

# Sample size calculation:

The sample calculation has been done for the **initially proposed primary endpoint (cohort 1)** and it's based on a Fleming's Single Stage Procedure:

We want to show that the Intracranial response rate by modified RECIST 1.1 before local treatment is superior or equal to the reference value, say, 90=40%. Under the hypothesis to have a response rate under new treatment ( $\pi$ 1) of 60% with  $\alpha$  risk = 5% in one-sided test and a power of 80%, the required sample size is 38 patients.

Finally, assuming that, 20% of patients will be lost of follow up, die or progress before day 56 without doing the first tumour assessment (according data published in COMBI-MB study), the initial sample size will be 48 patients, to obtain 38 evaluable patients.

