performed within 6 months after database closure expected at 24 months after last patient inclusion, however interim analysis might be performed when analysing other primary variables

Percentage of patients (%) free of extracraneal progression at 6 (week 24), 12 (week 28) and 24 months (week 96): percentage of patients free of progression by RECIST 1.1 at 6 months (week 24), 12 months (week 48) and 24-month (week 96) considering date of inclusion. The final statistical analysis of this endpoint is expected to be performed within 6 months after database closure expected at 24 months after last patient inclusion, however interim analysis might be performed when analysing other primary variables.

**Overall Survival in both cohorts (OS):** OS is calculated as the time from date of inclusion to date of death due to any cause. The final statistical analysis of this endpoint is expected to be performed within 6 months after database closure expected at 24 months after last patient inclusion, however interim analysis might be performed when analysing other primary variables.

Percentage of patients (%) alive at 6, 12 and 24 months in both cohorts: percentage of patients alive at 6 months, 12 month and 24-month considering date of inclusion. The final statistical analysis of this endpoint is expected to be performed within 6 months after database closure expected at 24 months after last patient inclusion, however interim analysis might be performed when analysing other primary variables.

**Toxicity of the combination until local treatment:** Number of patients with adverse events and serious adverse events, changes in laboratory values, vital signs, electrocardiograms (ECGs), LVEF (MUGA (Multigated Acquisition Scan) / echocardiogram) and assessment of physician, dermatological and ocular examinations graded according to the National Cancer Institute (NCI) Common Terminology Criteria for Adverse Events (CTCAE) v 4.03 until local treatment (local treatment D1). It will be studied using descriptive statistics techniques, such as frequency tables and contingency tables. The final statistical analysis of this endpoint is expected to be performed within 6 months after database closure expected at 24 months after last patient inclusion, however interim analysis might be performed when analysing other primary variables.

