#### 10.6. Statistical analysis

For each categorical variable, the results will be summarized by frequencies and percentages. For each continuous variable, the results will be summarized by descriptive statistics such as median, range, and interquartile range or by means, standard deviations and 95% confidence intervals (CIs). For proportions, point estimates and exact 95% confidence intervals will be calculated. For time to event endpoints, Kaplan-Meier estimates at selected time points and corresponding curves will be presented. Time to event is derived relative to the first study treatment administration. Laboratory values will be expressed as the absolute values and as grading (ordinal categorical variables) according to NCI CTCAE v 4.03.

Treatment-emergent AE (AEs starting after the administration of study treatment and up to study completion) will be summarized by system organ class and preferred term. Grading will be presented by type and grade in tables showing frequency and percentage of the within-patient worst grades. In addition, grade ≥3 AEs will be summarized separately. Full analysis details will be outlined in the statistical analysis plan (SAP).

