# 4.6. INTRACRANIAL PROGRESSION-FREE SURVIVAL (IPFS).

Intracranial Progression-free survival (PFS), defined as the time from inclusion (first dose of treatment) until intracranial tumour progression (RECIST 1.1) or death. Patients without any of the previous events are censored at the date of the last available tumor assessment.

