# 4.6.1.ITT ALL PATIENTS: INTRACRANIAL PROGRESSION-FREE SURVIVAL (IPFS).

0 patient has been censored at time 0 due to lack of tumor assessments.

Table 72: iPFS (event). ITT All patients

PFS (event)	N	%	95%CI
Censored			
Event (PD/death)			
Total			

Table 73: Median iPFS. ITT All patients

	Median	95%CI
PFS		

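### SAP addendum 2.2–2.3 compares OS and iPFS by radiotherapy from inclusion or first dose, although protocol radiotherapy follows the day-56 scan, so the contrast is biased even if radiotherapy has no effect

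*Combined protocol and SAP*

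**What the plan says.** The addendum has two sections on this, "2.2. OS ON ITT ACCORDING TO RADIOTHERAPY" and "2.3. IPFS ON ITT ACCORDING TO RADIOTHERAPY" (Tables 6–11, Figures 25–26). Each gives event counts with Pearson's chi-squared, Kaplan-Meier medians and means, estimates at 6, 12, 18 and 24 months, and a curve, split only into No and Yes. SAP section 2 defines ITT as every included patient.

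The clock starts before radiotherapy. Protocol section 10.2: "OS is calculated as the time from date of inclusion to date of death due to any cause". SAP 4.6 has iPFS "defined as the time from inclusion (first dose of treatment) until intracranial tumour progression (RECIST 1.1) or death". Protocol 10.6: "Time to event is derived relative to the first study treatment administration".

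Protocol section 5.3 directs radiotherapy, after the day-56 scan, at "Patients with no CR and no PD in brain MRI per modified RECIST 1.1 criteria, and no PD in body per RECIST 1.1 criteria". Patients with PD at that scan stop study drug and are followed for OS. Complete responders continue study drug without mandatory radiotherapy. They may be irradiated at the investigator's discretion, and are to receive local treatment if they later progress only in the brain.

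Addendum Table 5 separates 'Yes (CR)' and 'No (CR)' from 'Yes' and 'No'. Tables 6–11 do not show that split. The available text gives no landmark, time-dependent exposure or restriction by day-56 response.

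**The concern.** Patients are grouped by something that happens after the clock starts, and that most can reach only by being alive and progression-free at day 56. Three mechanisms follow.

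- **Guaranteed time.** Patients who fail before or at the scan fall in 'No' by default, so 'Yes' is largely event-free up to day 56 by construction. This favours 'Yes'.
- **Selection by response.** Unirradiated complete responders, presumably the best-prognosis patients, also fall in 'No' if the ITT label is taken at face value. This favours 'No'.
- **Reversed order.** A complete responder irradiated after a brain-only PD could be counted 'Yes' for an iPFS event that preceded radiotherapy. The same could apply to a day-56 PD patient irradiated later. No available rule prevents either.

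Protocol section 3 says it is unknown whether local therapy after a non-complete response prolongs response. Addendum Tables 6–11 are the only tables in the available SAP text that compare outcome by radiotherapy, so readers may take them as evidence on that question.

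**Working it through.** **Planning figures.** The plan states no figure for this comparison. Its only number on early failure is in the sample-size section: "20% of patients will be lost of follow up, die or progress before day 56 without doing the first tumour assessment". That calculation reproduces: n = [(1.645·√0.24 + 0.842·√0.24)/0.20]² = 37.1, stated as 38; 38/0.80 = 47.5, stated as 48.

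**Guaranteed time alone.** Inputs: early failure e = 20% (protocol 10.1, set for cohort 1); median 5.6 months (overall PFS in the asymptomatic cohort of the dabrafenib–trametinib trial cited in section 3, a proxy for iPFS); day 56 = 1.84 months. Assumed: no CR, 85% uptake among patients event-free at day 56, no radiotherapy effect.

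- Hazard after day 56 = ln(0.80/0.50)/(5.6 − 1.84) = 0.125 per month.
- 'Yes' at 6 months = exp(−0.125 × 4.16) = 59.5%.
- 'No' is 20% early failures plus 0.80 × 0.15 = 12% unirradiated, so 'No' at 6 months = (0.12/0.32) × 59.5% = 22%.

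With e = 5%: hazard = ln(0.95/0.50)/3.76 = 0.171; 'Yes' = exp(−0.171 × 4.16) = 49%; 'No' = (0.1425/0.1925) × 49% = 36%. The gap falls from 37 to 13 points.

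**Censoring rule.** Protocol 10.2 censors for iPFS, on the day after inclusion, patients with no image beyond baseline. If all early failures are of this kind, they leave the risk set and 'No' becomes 59.5%, the same as 'Yes'. SAP 4.6.1 reads "0 patient has been censored at time 0 due to lack of tumor assessments", so the actual early-failure share may be well below 20%.

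**Adding complete responders.** Simplify to all non-CR/non-PD patients irradiated, and 'No' = early failures (e) + day-56 PD (d) + CR (c), as shares of all patients. For iPFS, with assumed post-scan medians of 5 months (non-CR) and 12 months (CR):

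Yes − No = 0.5^((t−1.84)/5) − c·0.5^((t−1.84)/12)/(e+d+c).

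Example at 6 months, e = 0.20, d = 0.10, c = 0.30: 0.562 − 0.5 × 0.786 = +0.17. When early failures are censored, e leaves the denominator. For OS, the assumed post-scan medians are 12 (irradiated), 20 (CR) and 4 months (day-56 PD), and early failures are treated as deaths by day 56, which overstates them.

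| Yes − No, percentage points | 6 mo | 12 mo | 18 mo | 24 mo |
|---|---|---|---|---|
| iPFS, 5% CR | +45 | +17 | +5 | +1 |
| iPFS, 30% CR | +17 | −3 | −9 | −9 |
| iPFS, 30% CR, early failures censored | −3 | −17 | −19 | −16 |
| OS, 5% CR | +52 | +41 | +29 | +21 |
| OS, 30% CR | +27 | +18 | +10 | +4 |
| OS, 30% CR (median 30 mo), e = d = 5% | +4 | −6 | −13 | −17 |

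Over wider grids (e 5–20% for iPFS and 2–20% for OS, d 5–15%, c 5–30%, several medians), the share of scenarios favouring 'No' at 6/12/18/24 months was:

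- iPFS, early failures as events (432 scenarios): 4/35/59/72%.
- iPFS, early failures censored: 24/60/76/83%.
- OS (864 scenarios): 2/10/21/31%.

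These shares show where the sign can change. They are not probabilities.

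**A landmark alone is not enough.** If 'No' after day 56 is mainly CR patients, with the same iPFS medians, the false gap 6 months after the landmark is 0.5^(6/5) − 0.5^(6/12) = 0.435 − 0.707 = −0.27. The contrast must also be confined to non-CR patients.

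**The case against.** The strongest reply is that this is an exploratory comparison: not a protocol objective, no hazard ratio planned, no bearing on the positive-study rule. That is true and limits the severity, but it does not make the curves interpretable.

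A second reply is that 'No' may keep its Table 5 meaning and exclude 'No (CR)'. The ITT label argues against this, but the available text does not settle it. If it is so, the pull from complete responders disappears and the bias favours 'Yes'. It is not removed.

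Third, the inputs are assumed. That stands for the size: CR share, CR prognosis and uptake are not in the documents.

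Three stronger readings are tempting and should not be drawn:

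- That patients failing by day 56 can only be 'No'. The documents do not rule out later radiotherapy being counted as 'Yes'.
- That the direction is unknowable throughout. Guaranteed time by itself always favours 'Yes', and early OS most likely does too.
- That 60% against 22% estimates the actual bias. It needs the full 20% early failure, all counted as events, and no CR. The censoring rule in 10.2 and the SAP 4.6.1 statement both point to something smaller.

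**Conclusion.** The concern holds. As written, Tables 6–11 and Figures 25–26 are biased even if radiotherapy does nothing. OS at 6–12 months most likely favours 'Yes'. The net direction is uncertain mainly for iPFS at 12–24 months, and it depends on the CR share and on how early failures are handled. The size could be tens of percentage points or close to nil, and the documents do not allow a single estimate. The primary endpoint and sample size are unaffected. The tables should be changed because they would otherwise be read as evidence on a question that the protocol itself calls open.

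A separate, smaller point: in SAP Tables 153 and 162 and addendum Table 12 (symptomatic against asymptomatic groups), chi-squared on event counts is the only test named in the available text. The figures are not visible, so a log-rank result there cannot be excluded. A test on counts ignores event timing and unequal follow-up.

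**What to change.** Remove the No/Yes Kaplan-Meier contrast and its chi-squared test from addendum Tables 6–11. Instead:

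- Report OS and iPFS descriptively from the day-56 assessment in patients alive and without PD, showing CR and non-CR patients separately and counting only radiotherapy given before any PD.
- Give a radiotherapy contrast only within non-CR patients, from a landmark late enough for radiotherapy to have been given (for example week 12), classified by radiotherapy already received, and only if enough patients are unirradiated.
- Label it non-randomised, exploratory and post hoc. SAP 3.5 already refers to database closure.
- Separately, in Tables 153 and 162 and addendum Table 12, use a log-rank test and a Cox hazard ratio with 95% CI.

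The cost is SAP wording and reprogramming of a few tables. The downside is that there may be no contrast to report, because radiotherapy is the protocol default for eligible non-CR patients. Suppose 63 patients, early failure 20% or 5%, CR 30% or 0% of those event-free, and 5% with extracranial-only PD (the CR and extracranial shares are assumed). Then 63 × 0.80 × 0.70 × 0.95 = 33.5 to 63 × 0.95 × 1.00 × 0.95 = 56.9 are eligible. At 85% uptake that leaves about 5 to 9 unirradiated. Having 10 would need uptake no higher than 1 − 10/33.5 = 70% to 1 − 10/56.9 = 82%. Description is therefore the realistic main output. Confounding by indication remains. So does a difference in how progression is detected, because protocol 10.3 treats intracranial lesions as non-evaluable after local treatment.
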